19.1.2. Therapeutic component

Under the original randomised study design (prior to protocol v6.0), those patients allocated via randomisation to observation provide a reference control rather than a formal randomised comparator group. The statistical considerations underpinning the therapeutic intervention evaluation are those of a single group trial with patients treated with pembrolizumab in both the randomised and non-randomised

trial components combined. The original design hypothesised frequencies of ctDNA+ and allocation to pembrolizumab as per the text and table outlined below. The revision in the design to close the randomised component has the potential to increase the number of patients commencing pembrolizumab. No redefinition of the criteria have been undertaken since the success criteria are determined by the number starting treatment and not the overall proportion available to receive treatment.

The rate of ctDNA positivity is prone to stochastic effects, and as such a range of effect sizes is presented. All patients in the screening cohort who are observed to have a positive ctDNA will be entered into the therapeutic component, therefore the eventual number entering that phase will only be defined as the trial progresses. The most likely incidence, on which the primary calculations were made, is for a 30% positivity rate during the first 12 months. Calculations use an A'Hern single-stage design within pembrolizumab treated patients, alpha=0.1, power=90%, unacceptable ctDNA clearance rate p0 (of 0.3) and minimum required level of efficacy p1 of approximately 0.5. The number of clearances to conclude the required level of success and width of the 95% confidence interval which could be detected around a proportion with ctDNA clearance of approximately 0.5 are given for each hypothesised rate of ctDNA positivity.

Rate of ctDNA positivity	No. ctDNA positive (of 150 in ctDNA surveillance phase)	No. randomised to receive pembrolizumab	р0	р1	No. successes required	Width of 95% confidence interval detectable around proportion of 0.5
45%	68	45	0.30	0.49	18	+/- 0.14
30%	45	30	0.30	0.54	13	+/- 0.17
24%	36	24	0.30	0.57	10	+/- 0.19

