19.3. Endpoint definitions

19.3.1. **Primary Endpoints**

ctDNA surveillance

• Positive ctDNA detection by 12 and 24 months from start of ctDNA surveillance. This will be calculated as the proportion of patients with ctDNA positivity by each time point from those with assessment performed at that time point. Proportions will be presented with associated exact 95% confidence intervals.

Therapeutic component

 Absence of detectable ctDNA or disease recurrence 6 months (24 weeks) after commencing pembrolizumab. This will be calculated as the proportion of patients without either detectable ctDNA or disease recurrence 6 months after commencing pembrolizumab. Proportions will be presented with associated exact 95% confidence intervals.

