19.5. Interim analyses and stopping rules

No formal interim analysis of efficacy will be performed however the IDMC will meet regularly (at least annually) to assess safety and tolerability and also to review the emerging data on ctDNA incidence to inform the anticipated overall size of the therapeutic trial (i.e. to ensure processes in place for sufficient drug supply etc.) and to determine the relevant success criteria for the above A'Hern design required.

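### The success threshold for 24 treated patients (10) should be 11: as printed, the type I error is 15.3%, not the stated 10%

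*Protocol*

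**What the plan says.** Section 19.1.2 of the protocol states the method: "Calculations use an A'Hern single-stage design within pembrolizumab treated patients". The parameters are "alpha=0.1, power=90%, unacceptable ctDNA clearance rate p0 (of 0.3) and minimum required level of efficacy p1 of approximately 0.5". A table then gives three scenarios for the rate of ctDNA positivity, each with the number on pembrolizumab, p0, p1, the successes required and a 95% interval half-width around a proportion of 0.5:

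- 45 patients, p1 0.49, 18 successes, ±0.14
- 30 patients, p1 0.54, 13 successes, ±0.17
- 24 patients, p1 0.57, 10 successes, ±0.19. The row begins "24% 36 24 0.30 0.57 10".

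The same section says the criteria were not redefined when randomisation was closed in v6.0, because they depend on how many patients start treatment. Section 19.5 asks the IDMC, as data on ctDNA incidence emerge, "to determine the relevant success criteria for the above A'Hern design required". For the primary endpoints, section 19.3.1 says: "Proportions will be presented with associated exact 95% confidence intervals".

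**The concern.** An A'Hern design uses exact binomial probabilities, so each row can be checked directly. The required number must be large enough that a drug with the unacceptable clearance rate of 0.30 reaches it no more than 10% of the time, and small enough that a drug at p1 reaches it at least 90% of the time. The third row appears to fail the first condition.

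The table supplies the decision threshold for the therapeutic primary endpoint, and it remains in force under v6.0. A threshold that is one too low would allow a positive conclusion from a result that does not meet the protocol's own error rate. The interval column raises a separate, smaller question: whether it was computed by the method the protocol commits to for reporting.

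**Working it through.** **Inputs, all from section 19.1.2.** p0 = 0.30, alpha = 0.10, power = 0.90, and n, p1 and the required number r from each table row. The section does not say that alpha is one-sided, but an A'Hern test is: success is declared when X ≥ r.

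**Formulas.** Type I error = P(X ≥ r | n, 0.30). Power = P(X ≥ r | n, p1). X is binomial.

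| n | r | p1 | Type I error | Power at p1 | Meets 0.10 / 0.90? |
|---|---|---|---|---|---|
| 45 | 18 (printed) | 0.49 | 0.0986 | 0.913 | yes |
| 30 | 13 (printed) | 0.54 | 0.0845 | 0.912 | yes |
| 24 | 10 (printed) | 0.57 | **0.1528** | 0.957 | **no** |
| 24 | 11 | 0.57 | 0.0742 | 0.904 | yes |

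The first two rows reproduce. Lowering either threshold by one would break alpha (17 of 45: 0.1642; 12 of 30: 0.1593), so each is the smallest valid value. The printed 10 of 24 is the equivalent of those invalid choices.

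**Which r does the row's p1 belong to?** The smallest p1 giving 90% power is:

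- n = 45, r = 18: 0.4842 (printed 0.49)
- n = 30, r = 13: 0.5335 (printed 0.54)
- n = 24, r = 11: 0.5675 (printed 0.57)
- n = 24, r = 10: 0.5265

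Rounded up to two decimals, the first three give the printed p1 exactly. With r = 10 the third row would show 0.53. The printed 0.57 therefore goes with 11.

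**Other readings tried for the 24-patient row.**

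- *More than r, rather than at least r.* This repairs the row (0.0742, 0.904), but power falls to 0.855 in the 45-patient row and 0.839 in the 30-patient row. It cannot be the table's convention.
- *Normal approximation.* Cut-off 24 × 0.30 + 1.2816 × √(24 × 0.21) = 10.08, or 10.58 with continuity correction. Both round up to 11.
- *Two-sided alpha of 0.10.* The cut-off is 10.89, again 11.
- *A different n.* r = 10 is valid at n = 22 (0.0916; power 0.904 at 0.57) but not at n = 23 (0.1201). The 10 may have been carried over from n = 22; that is a conjecture.

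**Interval half-widths at a proportion of 0.5** (22 or 23 of 45, 15 of 30, 12 of 24):

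| n | Printed | Wald | Wilson | Exact (Clopper–Pearson) |
|---|---|---|---|---|
| 45 | 0.14 | 0.146 | 0.140 | 0.153 |
| 30 | 0.17 | 0.179 | 0.168 | 0.187 |
| 24 | 0.19 | 0.200 | 0.186 | 0.209 |

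The printed column agrees with Wilson score intervals. The exact intervals are wider in every row, by 0.01 to 0.02.

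**The case against.** The error is confined to the low-incidence scenario. The primary planning row (30 patients) is correct, and the 24 comes from the superseded 2:1 allocation of 36 positives, all of whom would now be allocated to treatment. The protocol says the final number will emerge during the trial, and an IDMC that applied the stated design afresh at n = 24 would arrive at 11. All of this limits how likely the wrong figure is to be used. It does not make the figure right: the criteria are expressly retained, and anyone reading the threshold from the table would use 10.

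The interval column can be defended as approximate planning precision with no method named. The half-width for the screening cohort in section 19.1.1 is likewise approximate (1.96 × √(0.21/150) = 0.073). The differences are small and change no decision. That makes this a matter of description, but the column still promises more precision than the reported intervals will have.

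Stating a general rule controls alpha but does not guarantee power. At 14 patients (threshold 7) and 18 patients (threshold 9), 90% power needs a true clearance rate of about 0.63 and 0.62, and power at 0.5 is only about 0.60 and 0.59. At 24 patients, moving from 10 to 11 lowers power at 0.5 from 0.85 to 0.73. This objection stands and should be disclosed alongside the rule. It is not a reason to keep 10, because the row's stated p1 is 0.57, where 11 still gives 90.4%.

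**Conclusion.** The concern holds. For 24 treated patients the threshold of 10 carries a type I error of 15.3% against the stated 10%, about one and a half times as large (0.153/0.10 = 1.53). The value that satisfies both stated error rates, and fits the row's own p1, is 11. This rests on exact binomial probabilities, p0 = 0.30 and the one-sided test inherent in the design, with success declared at or above the tabulated number. The rows for 30 and 45 patients are correct, and the consequence arises only if the number starting pembrolizumab is 24, or close to 24 with that row borrowed. Because this is a decision threshold for a primary endpoint, it should be corrected before analysis. The interval column is a secondary inconsistency that understates exact half-widths by up to 0.02.

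**What to change.** In the section 19.1.2 table, change the successes required for 24 patients from 10 to 11.

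Add the rule behind the table: for n patients starting pembrolizumab, the threshold is the smallest r with P(X ≥ r | n, 0.30) ≤ 0.10. This reproduces the two correct rows and covers numbers between and outside them: 7 of 14, 9 of 18, 10 of 22, 11 of 24, 13 of 30, 15 of 36, 18 of 45. Refer to the rule in section 19.5, so that the IDMC's determination follows from n alone. Give with each threshold the p1 at which power is 90%, so that the loss of power at small n is visible.

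Restate the interval column with exact half-widths (0.15, 0.19 and 0.21 for 45, 30 and 24 patients), or name the approximation used.

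The cost is one corrected table and a sentence or two in the protocol and SAP. No sample size changes; with 24 patients, one more clearance is needed to declare success.

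### The 95% interval half-widths stated for the clearance endpoint (Protocol 19.1.2) are 1 to 2 percentage points narrower than the exact interval prescribed in 19.3.1 will give

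*Protocol*

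**What the plan says.** Section 19.1.2 (Therapeutic component) sets out an A'Hern single-stage design with alpha 0.1, power 90%, p0 of 0.3 and p1 of about 0.5. For each hypothesised rate of ctDNA positivity it gives the number of clearances required and the "width of the 95% confidence interval which could be detected around a proportion with ctDNA clearance of approximately 0.5". Its table has three rows, one for each rate. The last column is headed "Width of 95% confidence interval detectable around proportion of 0.5". Reading across (positivity rate, number ctDNA positive, number on pembrolizumab, p0, p1, successes required, half-width), the rows are:

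- "45% 68 45 0.30 0.49 18 +/- 0.14"
- "30% 45 30 0.30 0.54 13 +/- 0.17"
- "24% 36 24 0.30 0.57 10 +/- 0.19"

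No interval method is named in the table or in the text around it.

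Section 19.3.1 (Primary Endpoints) defines the therapeutic primary endpoint: "This will be calculated as the proportion of patients without either detectable ctDNA or disease recurrence 6 months after commencing pembrolizumab". For its analysis it states: "Proportions will be presented with associated exact 95% confidence intervals".

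**The concern.** Both sections concern a 95% interval for the same proportion, and 19.3.1 says how that interval will be calculated. A reader will therefore take the table as the precision that the prescribed analysis will give. It is the protocol's only precision statement for this endpoint. If the widths come from a narrower type of interval, the reported interval will be wider than the protocol says in every scenario, and always in the unfavourable direction.

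**Working it through.** **Inputs.** From the 19.1.2 table: n = 45, 30 and 24; proportion 0.5; confidence level 95% (z = 1.96); stated half-widths 0.14, 0.17 and 0.19. From 19.3.1: the interval is to be exact, taken here as Clopper-Pearson.

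**Step 1: reproduce the stated figures.** The Wilson half-width is z·sqrt(p(1−p)/n + z²/(4n²)) / (1 + z²/n). With p = 0.5 and z² = 3.8415:

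- n = 45: 1.96 × sqrt(0.25/45 + 3.8415/8100) / (1 + 3.8415/45) = 0.140
- n = 30: 1.96 × sqrt(0.25/30 + 3.8415/3600) / (1 + 3.8415/30) = 0.168
- n = 24: 1.96 × sqrt(0.25/24 + 3.8415/2304) / (1 + 3.8415/24) = 0.186

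These round to 0.14, 0.17 and 0.19, the stated column.

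**Step 2: the exact interval.** For x successes in n, the lower limit is the 2.5% quantile of Beta(x, n−x+1) and the upper limit is the 97.5% quantile of Beta(x+1, n−x). The half-width is half the distance between them.

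- n = 45 (0.5 is not attainable, so take the two nearest counts): 22/45 gives 0.337 to 0.642 and 23/45 gives 0.358 to 0.663. Both have half-width 0.153.
- n = 30: 15/30 gives 0.313 to 0.687, half-width 0.187.
- n = 24: 12/24 gives 0.291 to 0.709, half-width 0.209.

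**Step 3: compare methods at 0.5.**

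| Method | n = 45 | n = 30 | n = 24 | Rounds to the stated column? |
|---|---|---|---|---|
| Stated | 0.14 | 0.17 | 0.19 | |
| Exact (Clopper-Pearson) | 0.153 | 0.187 | 0.209 | No, in no row |
| Normal approximation, z·sqrt(0.25/n) | 0.146 | 0.179 | 0.200 | No, in no row |
| Wilson | 0.140 | 0.168 | 0.186 | Yes |
| Agresti-Coull (equals Wilson at 0.5) | 0.140 | 0.168 | 0.186 | Yes |
| Jeffreys | 0.142 | 0.172 | 0.190 | Yes |
| Mid-P | 0.144 | 0.1747 | 0.194 | Yes, narrowly for n = 30 |

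Every method that reproduces the column is narrower than the exact interval.

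**Step 4: size of the gap.** Exact minus stated:

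- n = 45: 0.153 − 0.14 = 0.013
- n = 30: 0.187 − 0.17 = 0.017
- n = 24: 0.209 − 0.19 = 0.019

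Rounding to two decimals allows at most 0.005. As a share of the exact half-width the stated figures are about 8 to 9% too small; as a share of the stated figures the exact ones are about 9 to 10% larger.

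**Step 5: does the wording of approximately 0.5 explain it?** At counts close to each row's p1 (22/45, 16/30, 14/24) the exact half-widths are 0.153, 0.187 and 0.206. At each row's required number of successes (18/45, 13/30, 10/24) they are 0.150, 0.186 and 0.206. None rounds to the stated value.

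**The case against.** The strongest reply is that 19.1.2 gives approximate planning precision while 19.3.1 governs reporting, and that planning with an approximate interval and reporting an exact one is common. The screening component follows the same pattern: the +/-7.3% in 19.1.1 is the normal-approximation half-width for 30% of 150, where the exact figure at 45/150 is 7.6%. The numbers treated come from hypothesised positivity rates, and none was chosen to reach a target width. The final analysis is correctly specified and will report the right interval whatever this column says. All of that stands, and it limits the importance of the point. It does not make the column right: the figures are not labelled as approximate or tied to a method, and the prescribed interval gives none of them.

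The word exact in 19.3.1 does not name Clopper-Pearson, and mid-P, which is built from binomial tail probabilities, does round to the stated column. By convention, though, an exact interval for a proportion means Clopper-Pearson.

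Two stronger readings are tempting and are not supported:

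- A reader might infer that the planning method was Wilson. The column cannot show this, since Agresti-Coull, Jeffreys and mid-P also round to it.
- A reader might note that at 12/24 the exact lower limit is 0.291, below p0 = 0.30, while the stated width implies 0.50 − 0.19 = 0.31, and infer that the success decision is affected. The protocol never requires the 95% lower limit to exceed p0. Success is a count, and at the required counts the lower limit is below 0.30 under either method: 18/45 gives 0.257 exact and 0.270 Wilson; 13/30 gives 0.255 and 0.274; 10/24 gives 0.221 and 0.245.

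**Conclusion.** The point holds, and it is minor. For the exact interval that 19.3.1 prescribes, the half-widths in the 19.1.2 table are too small in all three rows, by 1 to 2 percentage points and by more than rounding allows. The error is confined to the stated precision: the success counts, the sample size and the go/no-go decision do not depend on the column. The conclusion assumes that exact means Clopper-Pearson and that the widths are meant as half-widths at, or close to, a proportion of 0.5, as the column heading says.

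**What to change.** In the table in 19.1.2, restate the last column as +/-0.15 (n = 45), +/-0.19 (n = 30) and +/-0.21 (n = 24), and say that these are exact (Clopper-Pearson) half-widths, in line with 19.3.1. Leave the analysis interval in 19.3.1 unchanged; altering a prespecified analysis to fit a planning column would be the wrong way round. The cost is three numbers and a few words in one table. The stated precision becomes slightly less favourable, and nothing else in the design changes.

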1.2.1. Rationale for study design

Selection of patients for treatment on the basis of a positive ctDNA test

Although assays of MRD are standard in the management of haematological cancers, this will be one of the first studies to assess whether ctDNA assays have clinical utility in guiding further therapy. Patients recruited into the c-TRAK TN study will be of moderate or high risk of future relapse. The inclusion criteria, on which risk for relapse are based, are similar to many previous adjuvant therapy studies for breast cancer (for example, BEATRICE NCT00528567 [16]) that have randomised all patients unselected to treatment or placebo. However, in these studies many patients never relapse, are consequently treated unnecessarily, and do not contribute to the primary endpoint of the study. In c-TRAK TN we will use assays of ctDNA to further select from within this population a set of patients who are at very high risk of relapse (i.e. those with a positive ctDNA test).

Prior to the implementation of protocol v6.0 during the original randomised component of the trial, this high risk population was randomised between intervention with medicinal product or observation. The standard of care for these patients is observation, and no treatment will be withdrawn as a result of ctDNA testing.

In protocol version 6.0, following recommendations made by the c-TRAK TN IDMC (further detail provided in the paragraph below), the trial design changed into the non-randomised component; randomisation was removed and all patients with a positive ctDNA result will be allocated to intervention with pembrolizumab. Patients who were previously randomised to observation and are continuing with ctDNA surveillance, will be asked to re-consent and subsequently be allocated to pembrolizumab at the next positive ctDNA test.

Rationale for the change in study design – June 2020 (protocol v6.0)

Study progress to date has provided data enhancing the evidence that ctDNA presence in the blood of patients treated for moderate and high risk TNBC is a definitive positive predictor of disease recurrence. In addition to this, data from external sources and emerging data from this trial suggest that instances of overt metastatic disease in these patients presents more frequently than initially predicted at study onset, that

c-TRAK TN Protocol

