3.2. Therapeutic Trial

Patients who have positive detection of ctDNA on or before their 12 month ctDNA surveillance assessment will be allocated to pembrolizumab treatment within the therapeutic trial centrally by ICR-CTSU.

Prior to the implementation of protocol v6.0 during the randomised component of the trial, patients who had positive detection of ctDNA on or before their 12 month ctDNA surveillance assessment were randomised centrally by ICR-CTSU in a 2:1 ratio to pembrolizumab treatment or observation (continued blinded ctDNA surveillance).

All patients randomised to observation prior to implementation of protocol v6.0 who remain in ctDNA surveillance, will transition to the non-randomised trial component following re-consent, and be allocated to pembrolizumab at the next positive ctDNA result.

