Under the original randomised study design (prior to protocol v6.0), of 150 patients screened, approximately 70% will remain ctDNA negative and 10% will be allocated to the observation group in the therapeutic trial (with the remaining 20% allocated to pembrolizumab in the therapeutic trial). Therefore assuming a 7:1 allocation ratio between groups 1) and 2) described above, a hazard ratio of 3.02 (assuming a reduction in 2 year relapse free rate from 80% to 51%) can be detected with 80% power, alpha 5% (two sided). We note that the HR demonstrated in retrospective testing for the ctDNA assay was 13.6, and the trial will be well powered for prospective validation.

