In prior research no patients with ctDNA detected at baseline spontaneously cleared ctDNA thus it is anticipated that such clearance would demonstrate activity of the intervention. The reference group in the randomised component of the trial will however provide further evidence to support that assertion. The number of patients randomised to the observation group (prior to the implementation of protocol v6.0) who have spontaneous clearance will be recorded and will be presented together with an associated 95% confidence interval to illustrate the likely theoretical upper bound of such an occurrence. Patients who subsequently receive pembrolizumab after transitioning to the non-randomised component of the trial will be excluded from this analysis if they start treatment within 24 weeks of becoming ctDNA positive and are therefore not assessable for the ctDNA clearance endpoint.

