19.3.2. Secondary Endpoints

Secondary endpoints relating to the observation group will be analysed in the patients randomised to the observation group prior to the implementation of protocol v6.0.

ctDNA surveillance

1) Time to ctDNA detection. This will be calculated as the time from entry into the ctDNA surveillance to first positive ctDNA detection. Statistical techniques for time to event data will be used to summarise data and display the pattern of ctDNA detection graphically.

Therapeutic component

- Detection of overt metastatic disease at the time of first ctDNA detection in patients allocated to pembrolizumab. This will be calculated as the proportion of patients with metastatic disease from CT scan at the same time point as first positive ctDNA detection, and presented with associated exact 95% confidence interval.
- 2) Lead-time between ctDNA detection and recurrence in the pembrolizumab treatment and observation groups. This will be calculated as the time between therapeutic trial entry and first confirmed detection of recurrent disease. Recurrence will include loco-regional and distant recurrence, but will exclude new primary cancers. Statistical techniques for time to event data will be used to summarise data and display time between ctDNA detection and recurrence graphically.
- 3) Absence of detectable ctDNA or disease recurrence after 6 months in the observation group. This will be calculated as the proportion of patients without either detectable ctDNA or disease recurrence 6 months after randomisation to the observation group. Proportions will be presented with associated exact 95% confidence intervals.
- **4)** Safety and tolerability of pembrolizumab in this patient group. Safety will be assessed throughout the treatment period using the NCI CTCAE v4.0 and summarised in tabular format. Reported toxicities

will be coded using Med DRA (current version). The proportion of patients reporting a dose reduction/delay during pembrolizumab will be presented.

5) Commencement of treatment in patients allocated to receive pembrolizumab. This will be calculated as the proportion of patients allocated to receive pembrolizumab who start this therapy. The proportion will be presented with associated exact 95% confidence interval.

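### The spontaneous-clearance reference drops observation patients who start pembrolizumab within 24 weeks, but only a further positive ctDNA result lets them start, so the estimate and its upper limit are biased upward

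*Protocol*

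**What the plan says.** Section 19.1.2 keeps the observation group as supporting evidence that ctDNA does not clear without treatment. The number of spontaneous clearances is to be shown with a 95% confidence interval "to illustrate the likely theoretical upper bound of such an occurrence". Observation patients who transfer to the non-randomised component "will be excluded from this analysis if they start treatment within 24 weeks of becoming ctDNA positive", because they "are therefore not assessable for the ctDNA clearance endpoint".

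Section 3.2 states how these patients reach treatment: after re-consent they will "be allocated to pembrolizumab at the next positive ctDNA result". Sections 1.2.1, 3.2.2 and 17 say the same.

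Section 19.3.2 defines essentially the same quantity as a secondary endpoint, the "proportion of patients without either detectable ctDNA or disease recurrence 6 months after randomisation to the observation group". It states no exclusion, and it counts time from randomisation rather than from becoming ctDNA positive.

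On size, section 19.1.1 expects that of 150 patients "10% will be allocated to the observation group in the therapeutic trial".

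**The concern.** Whether a patient is excluded depends on a ctDNA result obtained inside the window over which clearance is judged. An observation patient whose re-tests are negative has no route to pembrolizumab and stays in the analysis. One who is positive again may start pembrolizumab and then leaves it. The exclusion takes patients out of the denominator and cannot take a clearance out of the numerator, so the exclusions are informative and act in one direction.

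The upper confidence limit is what this analysis is meant to deliver. If the rule raises that limit, the group gives weaker support to the statement that spontaneous clearance is rare, although the discarded patients each have a positive sample taken before any pembrolizumab.

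**Working it through.** **1. Can the rule apply in practice?** Surveillance samples are 3-monthly, about 13 weeks apart, give or take 2 weeks (section 7.2.2). Treatment should start within 4 weeks of the site being notified (section 9.3). So 13 + 4 = 17 weeks, which leaves 7 weeks of the 24 for laboratory turnaround and delays. The rule can apply.

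**2. Who is removed?**

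| Observation patient after transfer | Starts pembrolizumab? | In the section 19.1.2 analysis? |
|---|---|---|
| Re-tests negative | No | Kept |
| Positive again, macroscopic disease on imaging | No (section 9.3) | Kept, as a failure |
| Positive again, declines or is ineligible | No | Kept |
| Positive again, starts within 24 weeks | Yes | Removed |

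The only row removed consists of patients with a further positive result. With x clearances among n patients and k removed, the reported proportion moves from x/n to x/(n − k).

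**3. Planned size.** Positivity is taken as 30% and allocation was 2:1, so the observation share is 0.30 × 1/3 = 10%, and 150 × 0.10 = 15. This reproduces the figure in section 19.1.1. The section 19.1.2 table agrees: 45 − 30 = 15, and its other rows give 68 − 45 = 23 and 36 − 24 = 12.

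**4. Upper limit with no clearances.** The exact two-sided 95% upper limit for 0 of m is 1 − 0.025^(1/m). The protocol does not give k, so the values below are assumptions.

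| Removed (k) | Kept (m) | Upper limit |
|---|---|---|
| 0 | 15 | 21.8% |
| 1 | 14 | 23.2% |
| 2 | 13 | 24.7% |
| 3 | 12 | 26.5% |
| 4 | 11 | 28.5% |
| 5 | 10 | 30.8% |

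With the other planned sizes and 3 removed, the limit goes from 26.5% to 33.6% (n = 12) and from 14.8% to 16.8% (n = 23).

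**5. With one clearance and n = 15.** All kept: 1/15 = 6.7%, upper limit 31.9%. Three removed: 1/12 = 8.3%, upper limit 38.5%. Five removed: 1/10 = 10.0%, upper limit 44.5%.

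**6. How many are likely?** Section 1.2.1 dates v6.0 to June 2020, and section 3 dates the suspension of surveillance to 19 March 2020. Assume that sampling largely stopped then and that no crossover treatment began before 1 July 2020. First positivity must then fall between about 15 January (24 weeks before 1 July) and 19 March 2020. For a patient first positive on 19 March, the window closes on 3 September 2020. Re-consent, a new positive result and the start of treatment must all fit before it closes. Few patients are likely to qualify.

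**The case against.** The strongest reply is that the endpoint is status at one time point, about 24 weeks. A positive re-test at about 13 weeks is not that outcome. Once pembrolizumab starts, untreated status at week 24 cannot be observed, so calling these patients not assessable is literally correct. Exclusion also depends on re-consent, eligibility, a clear scan and timing. All of this stands: a reader might infer that the rule removes patients known not to have cleared at 24 weeks, and the protocol does not support that. What is known is that they were positive again before treatment. The direction of the selection is unaffected.

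Counting them as failures also creates an asymmetry. Under section 19.3.1 a pembrolizumab patient positive at week 12 and clear at week 24 is a success, while an observation patient positive at re-test who then crosses over would be a failure. That leans slightly in the drug's favour, whereas the present rule leans the other way. This stands as a cost of the change, and is why both versions should be shown.

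Finally, if nobody clears, the point estimate is 0% under either rule and the count of clearances is unchanged. In that case only the upper limit moves, but the upper limit is the figure that section 19.1.2 sets out to show.

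**Conclusion.** The exclusion is informative. It removes only patients with a further positive result, so it biases the spontaneous-clearance proportion (once there is any clearance) and its upper 95% limit upward. For the planned 15 patients and no clearances, the upper limit rises from 21.8% to between about 23% and 31% for 1 to 5 exclusions. That range is assumed, and the dates point to its lower end. The actual size of the observation group is not stated either.

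Two stronger readings are tempting. The first is that the rule flatters pembrolizumab. It does the opposite: overstating spontaneous clearance is conservative for the drug claim. The second is that an upper limit above p0 = 0.30 undermines the design. No section compares this limit with p0. Section 19.1.2 calls the observation patients a reference rather than a formal comparator, and only the fifth assumed exclusion takes the limit past 0.30 (28.5% with four). No formal decision rule changes. The loss is in the strength of the supporting evidence, and because the protocol itself fixes the rule, it should be corrected there.

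**What to change.** Amend section 19.1.2 so that the main reference estimate keeps every patient randomised to observation in the denominator. Patients who are ctDNA positive again before starting pembrolizumab within 24 weeks are counted as not spontaneously cleared. Report the exclusion version as a sensitivity analysis, with the number excluded. Reconcile sections 19.1.2 and 19.3.2 on the denominator and on the time origin (becoming ctDNA positive versus randomisation).

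This takes one or two sentences and needs no new data, visits or patients. The cost is that a patient who might have cleared untreated between the re-test and week 24 is counted as not cleared, which slightly favours the drug. The report should say so.
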